5. OBJECTIVES

5.1 *General Objective*

To evaluate differences in the response of weight, body composition and metabolic biochemical parameters among obese patients following a normoprotein low-fat controlled ketogenic diet compared to a balanced BIEM).

5.2 *Specific Objectives*

- Intra- and intergroup comparison of patient weight and BMI reduction between baseline and subsequent follow-up monitoring visits.
- To determine the percentage of patients with weight loss equal to or greater than 10% of initial weight and the time it took for patients to reach this figure.
- Evaluate the evolution of comorbidities associated with obesity (HT, hyperglycemia or diabetes, hypercholesterolemia, hypertriglyceridemia, apneas), control of clinical and analytical parameters and changes in medication during the weight loss process and during follow-up.
- To know the tolerability of the diet: Incidence of side effects during the development of the study,
- Safety of the intervention diet: appearance of analytical alterations, especially of the ionic profile, renal function and hepatic function, incidence of serious adverse events.
- Assess diet adherence and dropout rate and cause.
- To know patient satisfaction with the assigned nutritional program.

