
occurs first. And new biochemical evaluations when the decrease of Ketone Bodies below 0.4 mmol/l is detected or when patients have reached a loss of 60 to 70% of their overweight and one more when they reach their weight loss goal. Subsequently, only clinical and nutritional follow-up will be given along with psycho-emotional support and physical activity advice every 3 months up to 12 months and every 6 months up to 24 months.

7.2 Study design.

Longitudinal, Prospective, Controlled Randomized Clinical Trial.

7.3 Study population.

Patients of either sex, between 18 and 60 years of age, with a body mass index (BMI) between 30 and 35 kg/m².

7.4 Sample.

The sample will be obtained by open call through social media and all patients who come with their clinical analysis and meet the inclusion criteria will be evaluated until the sample number is reached. In order to obtain 95% power in this Controlled Clinical Trial and with a 95% CI, a 3:1 case-control ratio is established, considering a 35% attrition rate, 56 cases and 32 controls will be included and subsequently crossed to become cases. (Calculated with EPIinfo STATCALC for sample size)

Two blinded arms are proposed for the physician and the patient.

Obese patients assigned to the low-fat normoprotein controlled ketogenic diet group.

Obese patients assigned to a balanced hypocaloric diet. And who will subsequently be subjected to a controlled normoproteic low-fat ketogenic diet.

7.5 Inclusion, exclusion and elimination criteria.

7.5.1 Inclusion:

- Men and Women
- 18 to 60 years of age
- With BMI between 30 and 35 Kg/m²
- Who has not taken weight loss treatment in the last 6 months

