Blood samples will be collected in Specialized Clinical Laboratories according to NOM-253-SSA1-2012 and the laboratory sample collection manual in force in each laboratory. A venous sample will be taken to determine Complete Blood Biometry, Blood Chemistry of 27 elements, Basic thyroid profile, Glycosylated

7.8 Measuring instruments.

With all the data, a database will be built in Excel MS®. Patient satisfaction will be measured with the Likert Scale, which consists of 5 possible answers per item: very satisfied, satisfied, indifferent, dissatisfied and very dissatisfied. (attached)

7.9 Statistical analysis.

Descriptive statistical tests will be performed establishing general and group measures, determining variability measures such as standard deviation and Confidence Interval, comparative inferential tests will be performed within and between groups, for quantitative variables it is proposed as an initial T-test, which will be contrasted according to the conditions of normality and homoscedasticity of the sample. For qualitative variables, χ^2 is initially proposed, which will be contrasted according to the same conditions; one-way ANOVA and repeated measures ANOVA will also be used. Microsoft Excel 365 and SPSS V 21

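### The between-arm tests use no baseline covariate and leave the outcome scale open, which costs precision: little for weight change, more for outcomes that track baseline less closely

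*Combined protocol and SAP*

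**What the plan says.** Section 7.9 of the combined protocol and SAP is the whole analysis plan. On continuous outcomes it says "for quantitative variables it is proposed as an initial T-test, which will be contrasted according to the conditions of normality and homoscedasticity of the sample", and then "one-way ANOVA and repeated measures ANOVA will also be used". It mentions no ANCOVA, regression, mixed model or covariate.

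The outcomes concerned are set in Section 5.1: "To evaluate differences in the response of weight, body composition and metabolic biochemical parameters among obese patients". For weight and BMI, Section 5.2 plans an "Intra- and intergroup comparison of patient weight and BMI reduction between baseline and subsequent follow-up monitoring visits", and H1 in Section 6 is worded as greater weight loss. For body composition and biochemistry no scale (final value or change) is given.

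Section 7.1 collects anthropometry, bioimpedance, a biochemical profile, a thyroid panel and blood gases at recruitment, before randomisation. Section 7.7 says patients are drawn by lot; no stratification on weight, BMI or sex is described. Section 7.4 plans "56 cases and 32 controls will be included and subsequently crossed to become cases", allowing for 35% attrition.

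**The concern.** The arms are small and unequal, and nothing in the design balances them on baseline. Nothing in the stated analysis uses baseline as a predictor either. In a trial of this size a visible chance difference in starting weight, fat mass or glucose is likely on at least some outcomes. A test that ignores baseline carries part of that difference into the estimate. It also leaves in the error term the variation that baseline could explain.

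The open scale adds to this. When baselines differ by chance, a comparison of final values and a comparison of changes are pushed in opposite directions. The plan does not say beforehand which will be reported for most outcomes. ANCOVA removes that choice, because with baseline in the model the arm difference is the same on either scale.

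**Working it through.** **Inputs from the documents.** 56 and 32 patients and 35% attrition (Section 7.4). If attrition is equal in both arms, 56 × 0.65 = 36.4 and 32 × 0.65 = 20.8, so about 36 and 21, or N = 57.

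**The plan's own figure.** The sample size cannot be reproduced, because no effect size, SD or event rate is given. The split 56/32 = 1.75:1 also differs from the 3:1 in Section 7.4 and the 2:1 in Section 7.1. That needs reconciling, but is a separate matter; only the counts are used here.

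**Assumptions.** The correlation r between baseline and follow-up is not in the documents, so a range is shown. SDs are taken as equal at both times.

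**Step 1: variance of the arm difference**, in units of the outcome variance:
- final values: 1
- change score: 2(1 − r)
- ANCOVA: 1 − r²

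So ANCOVA relative to change is (1 − r²)/[2(1 − r)] = (1 + r)/2, and relative to final values it is 1 − r².

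| r | ANCOVA / change | ANCOVA / final value |
|---|---|---|
| 0.5 | 0.75 | 0.75 |
| 0.7 | 0.85 | 0.51 |
| 0.9 | 0.95 | 0.19 |
| 0.95 | 0.975 | 0.098 |

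Against a change score, r = 0.5 to 0.7 is worth 1/0.75 = 1.33 to 1/0.85 = 1.18 times the patients. A change-score test with 80% power would rise to about 90% at r = 0.5, 86% at r = 0.7 and 82% at r = 0.9.

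**Step 2: cost of estimating the slope.** Expected variance is inflated by about 1 + 1/(N − 4) = 1 + 1/53 = 1.019. The net ratios against change become:
- r = 0.5: 0.75 × 1.019 = 0.764
- r = 0.7: 0.85 × 1.019 = 0.866
- r = 0.9: 0.95 × 1.019 = 0.968
- r = 0.95: 0.975 × 1.019 = 0.993

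The gain disappears at about r = 0.96, since (1 + 0.96)/2 × 1.019 is about 1.

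**Step 3: chance baseline difference.** Its SE is SD × √(1/n₁ + 1/n₂):
- 56 v 32: √(1/56 + 1/32) = 0.22 SD
- 36 v 21: √(1/36 + 1/21) = 0.27 SD

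The probability of a difference above 0.3 SD in either direction is 18% and 27% respectively. The second figure treats imbalance among completers as pure chance.

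**Step 4: how much stays in the estimate.** A fraction r stays in a final-value contrast. A fraction 1 − r stays in a change contrast, with opposite sign. For a 0.3 SD imbalance:
- r = 0.5: 0.15 SD on final values; 0.15 SD on change
- r = 0.9: 0.27 SD on final values; 0.03 SD on change

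**The case against.** The strongest reply is that the main question concerns weight loss, which the plan frames as reduction from baseline. Baseline is then already subtracted. A repeated measures ANOVA that includes the baseline visit would likewise test change through its group-by-time term. If r for weight is 0.9 or more, little is left to gain. This stands, and it limits the point for weight. It does not settle the other outcomes, for which no scale is given and r may be lower. Nor is subtracting baseline the same as adjusting for it.

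Some stronger readings are tempting and are not supported:

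- *Weight variance would fall to 0.19 at r = 0.9.* That compares ANCOVA with a test on final weights. Section 7.9 leaves the scale open, but Sections 5.2 and 6 point to change, where the ratio is 0.95.
- *Several kilograms of imbalance would stay in the weight result.* With an assumed SD of 12 kg, the SE of the raw baseline difference among completers is 0.275 × 12 = 3.3 kg. A change contrast keeps (1 − r) of it: about 0.33 kg at r = 0.9 and 0.16 kg at r = 0.95. These scale with the SD, which the documents do not give.
- *Adjustment is free and narrows every interval.* Step 2 shows a small cost at this size. The gain holds in expectation, and only where baseline predicts outcome.
- *Every quantitative outcome has a baseline value.* Time to 10% loss has none. Grip strength, vitamin D, CPK and C-reactive protein appear in Section 7.6 but are not named in the baseline list of Section 7.1.
- *The planned tests are biased or invalid.* Chance imbalance is not bias over repeated randomisation, and the lack of adjustment does not inflate type I error. The cost is precision, and a shift conditional on this trial's imbalance.

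**Conclusion.** The concern holds as a matter of efficiency and prespecification. Section 7.9 uses no baseline covariate and fixes no outcome scale, while the baseline data for the main outcomes are already collected. In large samples ANCOVA is at least as precise as either unadjusted test; how much better depends on r, which is assumed throughout.

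For weight analysed as change with r of 0.9 to 0.95, the net saving is about 1% to 3% of variance, which is small. For outcomes with r of 0.5 to 0.7 it is about 13% to 24% net against change scores. Against final values it is 25% to 49% before the slope cost. That laboratory values fall in this lower range is itself an assumption.

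The figures rest on equal SDs at both times and, for 36 v 21, on equal attrition in the arms. The change is worth making, but its absence does not invalidate the trial.

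**What to change.** Rewrite Section 7.9 as follows.

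1. **Weight, BMI and body composition.** Make the main between-arm comparison, at a prespecified visit before controls cross over, an ANCOVA with arm and the outcome's baseline value as terms. A mixed model for repeated measures, adding visit and arm-by-visit terms, is an alternative that can also use patients with missing visits. Either replaces the unadjusted t-test as the main comparison.
2. **Laboratory outcomes with a baseline value.** Use the same model, but state the comparison time point first. Under Section 7.1 follow-up samples are taken at weight-loss or ketone milestones, so no common week exists at present. Wording in Section 7.9 alone may not be enough here.
3. **Scale.** State for each outcome whether results are reported as final value or change. With baseline in the model the arm difference is the same either way.

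For the first group the cost is a few sentences, one degree of freedom and a little more analysis work. No extra patients or measurements are needed, and SPSS, already named in Section 7.9, fits these models.

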7.10 Description of treatments

7.10.1 Low-fat normoprotein Controlled Ketogenic Diet.

Patients randomly assigned to this group will undergo a standardized weight loss program under a nutritional intervention, physical exercise plan and emotional support.

The nutritional intervention is based on commercial preparations adjusted to 6 different stages.

Frank ketosis: the initial diet will consist of a very low calorie ketogenic diet (between 650 and 730 kcal/day) in 5 meal times, based on commercial and vegetable preparations with low glycemic index, an average of 1.2 g of protein/kg of ideal weight/day, 20 g/day of lipids based on essential fatty acids and less than 60 g/day of absorbable carbohydrates. Patients will also receive vitamin and trace element supplements (sodium chloride, magnesium oxide, calcium carbonate) to cover the daily requirements recommended for this type of diet. There is no stipulated time for this nutritional

intervention, the advance to the next stage is proposed as soon as the patient has lost 50% of his or her excess weight.

Mixed Ketosis: in this stage, one or two intakes of commercial preparations will be progressively replaced by proteins of natural origin (meat, fish, eggs, etc.), which will discreetly increase by 100 to 150 Kcal/day, without the patient 26.

Leaving the state of ketosis, the supplementation of vitamins and minerals will continue until the patient reaches 70% loss of excess weight.

Transition Stage: In this stage simple carbohydrates based on fruit and some complex carbohydrates in the form of cereals are added to the previous program, which allows the exit from the state of ketosis to enter a controlled hypocaloric diet of approximately 1300 to 1500 kcal/day to metabolically readapt to the consumption of macronutrients in an approximate proportion of 30 to 35% protein, 25% fat and 40 to 45 % carbohydrates. Patients will receive vitamin supplements to cover daily needs. Weight loss is not expected at this stage due to its short duration.

Integral and maintenance phase: during this stage the patient will follow a hypocaloric diet adapted to his measured energy expenditure, which may vary between 1300 and 2250 kcal/day, with a macronutrient distribution of 50% carbohydrates, 25% proteins and 25% fats, according to the Diogenes study (17), in this stage the process of dietary reeducation will be completed with a regimen in which the loss of 20 or 30% of the remaining excess weight is expected to be completed.

7.10.2 Hypocaloric Balanced Diet

Balanced hypocaloric diet (caloric intake 20% below basal metabolic expenditure measured by Multifrequency Bioelectrical Impedance or calculated according to the FAO/WHO/UN formula (FAO/WHO/UNU (1985). Energy and Protein requirements. Technical Report Series No 724, World Health Organization, Geneva). The usual caloric intake of a balanced hypocaloric diet is between 1,200 and 1,400 kcal per day with a macronutrient distribution of 50% carbohydrates, 25% proteins and 25% fats, according to the Diogenes study (17). 27

8. ETHICAL CONSIDERATIONS

In the present project, the ethical principles for medical research on human beings, established in the Declaration of Helsinki of the World Medical Association, in the General Health Law (Official Gazette of the Federation, 2015), in the Regulations of the General Health Law on Health Research and in the Mexican Official Standard NOM-012-SSA3-2012, will be specifically addressed. The research is considered with minimal risk according to the Regulation of the General Health Law on Health Research. It will be submitted to the Research Committees of the Institute of Health Sciences, and to the Research Ethics Committee. The informed consent process will be carried out by the researcher responsible for the project, requesting the patient's authorization for his/her participation. In the process of this project it is considered that the benefit will be greater than the risk, as well as the confidentiality of the patients will be kept at all times.

8.1. Informed Consent

Prior to inclusion in the study, all investigators must provide the patient with information about the study by means of the Patient Information Sheet (Appendix), propose participation in the study, answer any questions and ask the patient to fill in the Informed Consent Form (Appendix), which will be kept in the patient's own file.

8.2. Evaluation by an Ethics Committee

All materials from this study will be submitted to an accredited Clinical Research Ethics Committee (IRB) for evaluation. The study will be initiated once IRB approval has been obtained.

8.3. Confidentiality

The study data will be entered into an automated file owned by the promoter. The analysis of the results of the study will be made from the dissociated database, without personal data, so that no subject can be identified or identifiable.

9. Resources

9.1 Material and Financial Resources Zele \$2,484,000.00

Products

Appointments	\$729,000.00
In.Body	\$510,000.00
Computer Equipment	\$75,000.00
Dynamometers	\$2,260.00
Lab tests	\$572,184.00
Diagnostic reagents	\$35,000.00
Other	\$10,000.00
Total	\$4,417,444.00

